14.	PLA	NNED LISTINGS	19

Protocol: HZNP-ACT-303 Page 6 of 19

Final Version 1.0

ABBREVIATIONS

ABBREVIATION	DEFINITION OR DESCRIPTION
AE	Adverse Event
ATC	Anatomical Therapeutic Chemical
BSA	Body Surface Area
CI	Confidence Interval
CRF	Case Report Form
CSR	Clinical Study Report
ECG	Electrocardiogram
EMA	European Medicines Agency
FA	Friedreich's Ataxia
FARS	Friedreich's Ataxia Rating Scale
FARS-mNeuro	Friedreich's Ataxia Rating Scale excluding the peripheral nervous system
	subscale score and the facial and tongue atrophy and fasciculations from
	the bulbar subscale score
FARStot	Total FARS Score
FDA	Food and Drug Administration
ICH	International Conference on Harmonisation
LLOQ	Lower Limit of Quantitation
LOD	Limit of Detection
MedDRA	Medical Dictionary for Regulatory Activities
SAE	Serious Adverse Event
SAP	Statistical Analysis Plan
SD	Standard Deviation
SOC	System Organ Class
SOP	Standard Operating Procedure
TIW	Three times a week
TEAE	Treatment-emergent Adverse Event
ULOQ	Upper Limit of Quantitation
WHO-DD	World Health Organization Drug Dictionary

Protocol: HZNP-ACT-303 Page 7 of 19

Final Version 1.0

1. OVERVIEW

This Statistical Analysis Plan (SAP) describes the planned analysis and reporting for Horizon Pharma Ireland, Ltd. protocol HZNP-ACT-303 (Long-Term Safety Extension of ACTIMMUNE® (interferon γ-1b) in Children and Young Adults with Friedreich's Ataxia), Final Version 1.0 and Administrative Change 1, dated 21-Apr-2016.

The structure and content of this SAP provides sufficient detail to meet the requirements identified by the Food and Drug Administration (FDA), European Medicines Agency (EMA), and International Conference on Harmonization (ICH) of Technical Requirements for Registration of Pharmaceuticals for Human Use: Guidance on Statistical Principles in Clinical Trials [1]. All work planned and reported for this SAP will follow internationally accepted guidelines, published by the American Statistical Association [2] and the Royal Statistical Society [3], for statistical practice.

The planned analysis identified in this SAP may be included in clinical study reports (CSRs), regulatory submissions, or future manuscripts. Also, post-hoc exploratory analysis not necessarily identified in this SAP may be performed to further examine study data. Any post-hoc, or unplanned, exploratory analysis performed will be clearly identified as such in the final CSR.

In addition to the study protocol, the following documents were reviewed in preparation of this SAP:

- The electronic case report forms (eCRFs) for this Protocol
- ICH Guidance on Statistical Principles for Clinical Trials (E9).

The reader of this SAP is encouraged to also read the clinical protocol, and other identified documents, for details on the planned conduct of this study. Operational aspects related to collection and timing of planned clinical assessments are not repeated in this SAP unless relevant to the planned analysis.

2. STUDY OBJECTIVES AND ENDPOINTS

2.1 Study Objectives

2.1.1 Primary Objective

The primary objectives of this study are:

• To evaluate the long-term safety of ACTIMMUNE in subjects with Friedreich's Ataxia (FA).

2.2 Study Endpoints

The analysis for this study is for an abbreviated safety Clinical Study Report (CSR). All efficacy endpoints mentioned in the protocol have been removed and noted as changes to the planned analyses.

2.2.1 Safety Endpoints

Adverse event and concomitant medication data will be summarized. Clinical laboratory safety data, vital sign data, and ECG interval data will be summarized with descriptive statistics for

Protocol: HZNP-ACT-303 Page 8 of 19

Final Version 1.0

Baseline of HZNP-ACT-303, post-dose, and change from Baseline of HZNP-ACT-303 to post-dose values. Shift tables will be presented for clinical laboratory values and ECG categorical results from Baseline of HZNP-ACT-303 to each post-dose visit. Physical examination findings will be listed by subject.

3. OVERALL STUDY DESIGN AND PLAN

This is a multi-center, open-label, long-term safety extension study of ACTIMMUNE in the treatment of FA in children and young adults. Subjects who complete 26 weeks of treatment in HZNP-ACT-302 will be eligible for enrollment in this study. The sample size is not based on statistical considerations.

The overall maximum treatment duration for an individual subject is open-ended and treatment will continue until ACTIMMUNE is commercially available for the treatment of FA in the US or until the Sponsor decides to discontinue development for this indication. The initial dose of ACTIMMUNE will be individualized for each subject and will be determined by the investigator, provided that the initial dose does not exceed the maximum tolerated dose in HZNP-ACT-302. The investigator may subsequently adjust the dose for any subject if deemed clinically appropriate, provided that the dose does not exceed 100 μ g/m2. All doses of ACTIMMUNE will be administered by subcutaneous injection three times a week (TIW) at home.

Protocol: HZNP-ACT-303 Page 9 of 19

Final Version 1.0

Table 1.Schedule of Events

Study Phase	Treatment Period			End-of-Study
	Baseline ⁶	3-Month Visits ⁸	6-Month Visits	or Premature Withdrawal ¹⁰
Study Days (± visit window)	Day 1 (Week 28 of Study HZNP-ACT-302)	90 (± 7) Days after Last Visit	Every 180 (± 14) Days	
Informed consent/assent	X			
Medical history ¹	X			
Review of inclusion/exclusion criteria	X			
Dispense study drug ²	X	X^9	X	
Drug compliance ³		X^9	X	X
TEAE, SAE assessment ⁴	X^7	X	X	X
Brief physical examination	X^7		X	X
Vital Signs: blood pressure, pulse, temperature	X		X	X
Clinical laboratory evaluation (hematology, chemistry, urinalysis)	X		X	X
Electrocardiograms				X ¹¹
Urine pregnancy test ⁵	X		X	X
FARS				X ¹¹
Prior/concomitant medications	X^7	X	X	X

SAE=serious adverse event, TEAE=treatment-emergent adverse event.

- ³ Subjects will be instructed to return all used and unused study drug vials at each clinic visit.
- ⁴ Adverse events occurring or worsening on or after the date of administration of the first dose of study drug through the end of the study will be considered treatment-emergent adverse events (TEAEs). All serious adverse events (SAEs) that occur on or after the date of administration of the first dose of study drug through two weeks after study discontinuation will be considered treatment-emergent SAEs (TESAEs) and will be recorded and reported to Horizon drug safety.
- ⁵ Only for female subjects of childbearing potential.
- 6 The Day 1 Visit of this study (HZNP-ACT-303) occurs on the same day as the EOS Visit (Week 28 Follow-Up Visit) for HZNP-ACT-302.
- Findings will be recorded for both the Day 1 (Baseline) Visit of this study and the Week 28 Follow-up Visit for HZNP-ACT-302.
- Subjects who are not able to receive direct-to-home study drug shipments will return to the clinic for interim clinic visits three months after the Baseline and 6-month assessment visits; those who are able to receive direct-to-home shipments will be contacted by telephone.
- ⁹ Perform at clinic visits only; those with telephone visits will receive/return study drug supplies at next clinic visit.
- Subjects who complete the study will undergo final assessments while still on study drug and will then be transitioned to commercial product. Subjects who prematurely withdraw from the study will have the EOS assessments completed within two weeks of study drug discontinuation. In the event the Sponsor decides to discontinue development for the treatment of FA, all subjects will be contacted and instructed to return to the clinic for final assessments while still on active drug.

¹¹ For statistical purposes, the last on-treatment visit from HZNP-ACT-302 (Visit 26) will be used to assess changes to the EOS assessment in this study.

Changes in medical history from the Baseline of HZNP-ACT-301 will be recorded on the electronic case report forms. The medical history from the HZNP-ACT-301 study will be available for reference.

Subjects will be given a 3-month supply of study drug at each clinic visit and an additional 3-month supply will be directly shipped to the subjects' home in between the required 6-month clinic visits. If direct shipments are not feasible, subjects will return to the clinic every three months to obtain study drug; however, assessments (other than adverse event queries) will only be performed every six months.

Protocol: HZNP-ACT-303 Page 10 of 19

Final Version 1.0

4. ANALYSIS AND REPORTING

4.1 Interim Analysis

No formal interim analysis is planned for this study.

4.2 Final Analysis

All final, planned analysis identified in the protocol and in this SAP will be performed after the last subject has completed the End of Study Visit and all relevant study data have been processed and integrated into the analysis data base.

Any post-hoc, exploratory analysis completed to support planned study analysis, which were not identified in this SAP, will be documented and reported in appendices to the CSR. Any results from these unplanned analyses (post-hoc) will also be clearly identified in the text of the CSR.

5. ANALYSIS POPULATIONS

The following analysis populations are planned for this study:

• **Safety Population (SAFETY):** The Safety Population includes all subjects who receive at least one dose of open-label study drug after the Baseline Visit for HZNP-ACT-303. All analyses will be based on the Safety Population unless otherwise noted.

5.1 Sample Size

Subjects who complete 26 weeks of treatment in Study HZNP-ACT-302 will be eligible for enrollment. The sample size is not based on statistical considerations; therefore no inference will be drawn from any statistical tests conducted.

6. GENERAL ISSUES FOR STATISTICAL ANALYSIS

Data processing, tabulation of descriptive statistics, calculation of inferential statistics, and graphical representations will be performed using SAS® Software (release 9.3 or higher) for Windows, unless otherwise specified.

Continuous (quantitative) variables will be summarized using descriptive statistics including number of non-missing values, mean, standard deviation (SD), median, minimum, and maximum.

Categorical (qualitative) variables will be summarized using the number and proportion of each possible value. In general, the denominator for the percentage calculation will be based upon the total number of subjects in the study population for the treatment group.

The minimum and maximum will be reported with the same degree of precision (i.e., the same number of decimal places) as the raw data. Measures of location (mean and median) will be reported to 1 degree of precision more than the raw data and measures of spread (standard deviation) will be reported to two degrees of precision more than the raw data.

Assessments done on unscheduled visits will not be summarized but will be listed. All analyses will be completed on the Safety Population unless otherwise specified. Additionally, all summaries will be presented by overall treatment.

All final, planned analyses identified in the protocol and in this SAP will be performed after all relevant study data have been processed and integrated into the analysis database, analysis populations have been finalized, and the database has been locked. Any post-hoc, exploratory

Protocol: HZNP-ACT-303 Page 11 of 19

Final Version 1.0

analysis completed to support planned study analyses, which were not identified in this SAP, will be documented and reported in Section 9.8 of the CSR. Any results from these unplanned analyses (post-hoc) will also be clearly identified as subject in the text of the CSR.

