2.1 Schedule of Assessments

Study Phase	Treatment Period			End-of-Study or Premature Withdrawal ¹⁰
	Baseline ⁶	3-Month Visits ⁸	6-Month Visits	
Study Days (± visit window)	Day 1 (Week 28 of Study HZNP-ACT-302)	90 (± 7) Days after Last Visit	Every 180 (± 14) Days	
Informed consent/assent	X			
Medical history ¹	X			
Review of inclusion/exclusion criteria	X			
Dispense study drug ²	X	X ⁹	X	
Drug compliance ³		X ⁹	X	X
TEAE, SAE assessment ⁴	X ⁷	X	X	X
Brief physical examination	X ⁷		X	X
Vital Signs: blood pressure, pulse, temperature	X		X	X
Clinical laboratory evaluation (hematology, chemistry, urinalysis)	X		X	X
Electrocardiograms				X ¹¹
Urine pregnancy test ⁵	X		X	X
FARS				X ¹¹
Prior/concomitant medications	X ⁷	X	X	X

SAE=serious adverse event, TEAE=treatment-emergent adverse event.

¹ Changes in medical history from the Baseline of HZNP-ACT-301 will be recorded on the electronic case report forms. The medical history from the HZNP-ACT-301 study will be available for reference.

² Subjects will be given a 3-month supply of study drug at each clinic visit and an additional 3-month supply will be directly shipped to the subjects' home in between the required 6-month clinic visits. If direct shipments are not feasible, subjects will return to the clinic every three months to obtain study drug; however, assessments (other than adverse event queries) will only be performed every six months.

³ Subjects will be instructed to return all used and unused study drug vials at each clinic visit.

⁴ Adverse events occurring or worsening on or after the date of administration of the first dose of study drug through the end of the study will be considered treatment-emergent adverse events (TEAEs). All serious adverse events (SAEs) that occur on or after the date of administration of the first dose of study drug through two weeks after study discontinuation will be considered treatment-emergent SAEs (TESAEs) and will be recorded and reported to Horizon drug safety.

⁵ Only for female subjects of childbearing potential.

⁶ The Day 1 Visit of this study (HZNP-ACT-303) occurs on the same day as the EOS Visit (Week 28 Follow-Up Visit) for HZNP-ACT-302.

⁷ Findings will be recorded for both the Day 1 (Baseline) Visit of this study and the Week 28 Follow-up Visit for HZNP-ACT-302.

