8.5.2.5 Clinical Laboratory Tests

Samples of blood (4.5 mL) and urine are scheduled for collection at Baseline/Day 1, each 6-month assessment clinic visit, and the EOS (or PW) Visit. Additional follow-up samples for clinical laboratory testing should be obtained as clinically indicated.

All clinical laboratory testing, with the exception of on-site urine pregnancy tests during the treatment period for females of childbearing potential, will be performed by the central clinical safety laboratory (URMC).

The following clinical laboratory tests will be performed:

- Complete blood count
- Chemistry panel
- Urinalysis

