8.6.5 Sample Size and Power Considerations

Subjects who complete 26 weeks of treatment and the Week 28 Follow-Up Visit in Study HZNP-ACT-302 will be eligible for enrollment. The sample size is not based on statistical considerations.

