5.4 Hepatic Toxicity

Repeated administration of ACTIMMUNE to patients with advanced hepatic disease may result in accumulation of interferon gamma-1b. Frequent assessment of liver function in these patients is recommended.

Elevations of aspartate transaminase (AST) and /or alanine transaminase (ALT) (up to 25-fold) have been observed during ACTIMMUNE therapy. The incidence appeared to be higher in patients less than 1 year of age compared to older children. The transaminase elevations were reversible with reduction in dosage or interruption of ACTIMMUNE treatment. Patients begun on ACTIMMUNE before age one year should receive monthly assessments of liver function. If severe hepatic enzyme elevations develop, ACTIMMUNE dosage should be modified [see *Dosage and Administration (2.3)*].

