6.2 Data Adjustments, Handling, Conventions

All collected data will be presented in listings. Data not subject to analyses according to this plan will not appear in any tables or graphics but will be included only in the data listings.

Adverse events will be coded using the Medical Dictionary for Regulatory Activities (MedDRA) (version 16.1). Concomitant medications will be coded using World Health Organization Drug Dictionary (WHO-DD) (version March 1, 2013).

If partial dates occur, the convention for replacing missing dates for the purposes of calculating derived variables is as follows:

For partial start dates:

- If the year is unknown, then do not impute the date but assign a missing value.
- If the month is unknown, then:
 - o If the year matches the year of enrollment date, then impute the month and day of the randomization date.
 - o Otherwise, assign 01 January
- If the day is unknown, then:
 - o If the month and year match the month and year of the enrollment date, then impute the day of the first dose date.
 - o Otherwise, assign 01

For partial end dates:

- If the year is unknown, then do not impute the date but assign a missing value.
- If the month is unknown, then assign the last day of the year, 31 December.

If the day is unknown, then assign the last day of the month.

If an AE has a missing severity, it will be imputed as 'Severe'; any missing relationship to study drug of an AE will be imputed as 'Related'. No other missing data will be imputed unless otherwise specified.

In general, for quantitative laboratory values reported as '<' or '≤', the lower limit of quantitation (LLOQ), or limit of detection (LOD), the reported value (i.e., LLOQ, LOD) will be used for analysis).

For quantitative laboratory values reported as '>' or '\geq', the upper limit of quantitation (ULOQ), the reported value (i.e., ULOQ) will be used for analysis.

For analysis purposes, repeat laboratory test results will not be used unless the original laboratory value is missing or indicated as invalid, in which case the first non-missing repeat

Protocol: HZNP-ACT-303 Page 12 of 19

Final Version 1.0

laboratory value will be used for data analysis.

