9.2 Clinical Laboratory Evaluations

Descriptive summaries of actual (absolute) values and changes from baseline will be presented for Chemistry, Urinalysis, and Complete Blood Count. These tables will be grouped by visit, and overall treatment.

The number and proportion of subjects with clinical laboratory values below, within, or above normal ranges, at each study visit will be tabulated (shift tables) for each clinical laboratory analyte by treatment group. Normal ranges will be provided by the central laboratory (Eurofins Central Laboratory) used in this study.

Laboratory values will be displayed in data listings and those that are outside the normal range will be flagged, along with the corresponding normal ranges.

Protocol: HZNP-ACT-303 Page 15 of 19

Final Version 1.0

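### Unscheduled laboratory values, and repeats with a valid original, are left out of the laboratory tables, and no worst-post-baseline table brings their peaks back in

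*SAP*

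**What the plan says.** Protocol 8.5.2.5 has blood and urine samples "scheduled for collection at Baseline/Day 1, each 6-month assessment clinic visit, and the EOS (or PW) Visit"; the Schedule of Assessments sets the 6-month visits at "Every 180 (± 14) Days". The same section adds: "Additional follow-up samples for clinical laboratory testing should be obtained as clinically indicated". Protocol 8.5.2.1.6 asks for unexplained, clinically significant abnormal results to be repeated at once and followed until they return to the reference range or to the subject's baseline.

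The SAP handles these extra results by three rules:

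- Section 6: "Assessments done on unscheduled visits will not be summarized but will be listed".
- Section 6.2: "repeat laboratory test results will not be used unless the original laboratory value is missing or indicated as invalid"; in that exceptional case the first non-missing repeat is used.
- Section 9.2: descriptive summaries of values and changes grouped by visit, and a shift table: "The number and proportion of subjects with clinical laboratory values below, within, or above normal ranges, at each study visit will be tabulated".

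All laboratory values are listed, with out-of-range values flagged (SAP 9.2). The readable text describes no worst-post-baseline or threshold table.

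**The concern.** Long-term safety is the study's only objective (Protocol 7.1, SAP 2.1.1), and the SAP drops efficacy in favour of an abbreviated safety report. The laboratory tables are therefore a main numerical result of the study.

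The laboratory effects described in the label appended to the protocol can come and go. Neutropenia and thrombocytopenia are described as reversible (label 5.3). On liver enzymes, label 5.4 reports rises of up to 25-fold and says: "The transaminase elevations were reversible with reduction in dosage or interruption of ACTIMMUNE treatment". Protocol 6.2 reports that in the 12-subject pilot study two subjects had a lower maintenance dose than planned because of raised liver function tests and/or flu-like symptoms.

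With scheduled samples six months apart, a for-cause or repeat sample may be the only measurement of such an episode. At stake is whether the report can say, from a table, how many subjects ever had a marked abnormality and how large it was.

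**Working it through.** **No figure to reproduce.** The plan gives no power, precision or detection figure: "The sample size is not based on statistical considerations". The main check is to trace where each kind of result ends up.

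| Result | By-visit summary and shift table | Listing | TEAE tables |
|---|---|---|---|
| Scheduled, valid first result | Yes | Yes | If judged clinically significant |
| Unscheduled | No (SAP 6) | Yes | If judged clinically significant |
| Repeat, valid original exists | No (SAP 6.2) | Yes | If judged clinically significant |
| Repeat, original missing or invalid | First non-missing repeat | Yes | If judged clinically significant |
| Premature withdrawal (PW) | Mapped to closest scheduled visit (SAP 6.1) | Yes | If judged clinically significant |

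The last column follows from Protocol 8.5.2.1.1, where a laboratory abnormality counts as a TEAE if the investigator judges it clinically significant, and from SAP 9.1, which tabulates TEAEs by preferred term, severity and relationship.

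Two details follow:

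- If a value climbs on repeat, the tables keep the lower first result.
- If a PW value is mapped to a visit that already has one, SAP 6.1 uses the value nearest the scheduled time. The PW value may then drop out, possibly for a subject leaving because of toxicity.

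**How often scheduled samples alone would catch a transient abnormality.** Let T be the interval between scheduled samples (180 days) and d the length of the abnormality. The documents give no d, so it is an assumption. With onset uniform over the interval, P(overlap with a scheduled sample) = min(1, d/T).

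| d (days, assumed) | d/180 | Missed by schedule, 1 − d/180 |
|---|---|---|
| 7 | 3.9% | 96.1% |
| 14 | 7.8% | 92.2% |
| 28 | 15.6% | 84.4% |
| 60 | 33.3% | 66.7% |
| 90 | 50.0% | 50.0% |

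Reading the ±14-day window as an interval of 166 to 194 days changes little: 14/194 = 7.2% to 14/166 = 8.4%, and 60/194 = 30.9% to 60/166 = 36.1%.

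**What that does and does not size.** Let s be the chance that an abnormality missed by the schedule is sampled off schedule, and c the chance that one so sampled is judged clinically significant. Then:

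- share whose value is measured but enters no laboratory table = (1 − d/180) × s
- share that reaches no table at all = (1 − d/180) × s × (1 − c)

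The documents give neither s nor c. As s runs from 0 to 1, the first quantity runs from 0 to 92.2% for d = 14 and from 0 to 66.7% for d = 60. The second is smaller whenever c is above zero.

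**The case against.** A reader might infer that for-cause results never reach a table. The documents do not support that. Abnormalities judged clinically significant become TEAEs, Protocol 8.5.2.1.3 applies the severity grades to them expressly, and SAP 9.1 tabulates them. A rise that led to a dose change would ordinarily be among them, and the reason for every dose adjustment is recorded on the eCRF (Protocol 8.1). So it does not follow that the report as a whole would understate such a case. What the TEAE route does not give is the size of the abnormality, or a count of those not judged significant.

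A reader might also infer that 67% to 92% of abnormalities lasting 14 to 60 days would be visible only in unscheduled samples. That is the share the schedule misses under an assumed duration. A silent episode may prompt no sample, and no table can recover what was not measured.

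Three further points count for the plan:

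- The repeat rule keeps an abnormal scheduled result from being replaced by a later normal one.
- The shift table puts a small and a very large rise in the same cell, but the by-visit minimum and maximum (SAP 6) would show an extreme scheduled value.
- The severity scale is not purely symptomatic; it also refers to the need for further medical evaluation or treatment.

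The rises seen as early as 7 days after starting treatment (label 6.2) come from children treated before one year of age, whereas the SAP age categories begin at 10, so they say little about timing here.

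The report is descriptive and single-arm, with about four centres, so listings can plausibly be read subject by subject. That is fair, but a listing does not give an incidence. Finally, the list of planned tables is not readable in the copy reviewed, so the absence of a worst-value table rests on SAP 6, 6.2 and 9.2. The section 6 rule, as worded, would keep unscheduled values out of such a table anyway.

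**Conclusion.** The point holds in a limited form. The stated rules keep unscheduled values, and repeats with a valid original, out of every laboratory table. The loss is the numeric peak of off-schedule abnormalities, and any such abnormality not judged clinically significant. Its size cannot be fixed from the documents. The d/180 figures (8% at 14 days, 33% at 60) show only that six-monthly samples would usually miss a short episode; they rest on an assumed duration, uniform onset and one episode per interval. By-visit tables on scheduled values are sound in themselves. This is a cheap improvement to the reporting of a safety-only study and does not undermine the analyses already planned.

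**What to change.** 1. **SAP 6.** Change the rule on unscheduled assessments, for laboratory data, to: not summarized by visit, but included in worst post-baseline summaries. Leave the by-visit tables on scheduled values.
2. **SAP 6.2.** Add the matching exception, so that valid repeats count towards worst-post-baseline summaries even when a valid original exists.
3. **SAP 9.2.** Add a shift table per analyte from baseline to worst post-baseline value, using all valid results (scheduled, unscheduled, repeat and PW), each subject counted once, with low and high directions separate where both matter. For ALT, AST, neutrophils and platelets use magnitude categories, such as multiples of the upper limit of normal for the enzymes and numeric thresholds for the counts, fixed before the results are seen. Confirm that the panels report these analytes; the protocol names only a complete blood count, a chemistry panel and urinalysis.
4. **Define the period.** Start at the first HZNP-ACT-303 dose, because SAP 6.3 takes baseline from Week 26 of HZNP-ACT-302. State that the PW sample is included, since it may be drawn up to two weeks after the drug is stopped.
5. **Footnote.** Subjects sampled more often have more chances of an extreme value, so worst-value counts run somewhat high.

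The cost is a few lines of SAP text and one table layout on data already collected; no visit, sample or procedure changes. It should be done before results are seen, because SAP 1 and 4.2 require analyses not identified in the SAP to be labelled post hoc.
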